Annex V: Palliative Care Assessment Tools

Supportive and Palliative Care Indicators Tool (SPICT)

The SPICT is used to help identify people whose health is deteriorating. Assess them for unmet supportive and palliative care needs.

Look for any general indicators of poor or deteriorating health.

Status	Assessment Indicator
	Unplanned hospital admission(s).
	Performance status is poor or deteriorating, with limited reversibility. (eg. The person stays in bed or in a chair for more than half the day.)

	Depends on others for care due to increasing physical and/or mental health problems.
	The person's carer needs more help and support.
	Progressive weight loss; remains underweight; low muscle mass.
	Persistent symptoms despite optimal treatment of underlying condition(s).
	The person (or family) asks for palliative care; chooses to reduce, stop or not have treatment; or wishes to focus on quality of life.

Look for Clinical Indicators of Life-Limiting Conditions

Category	Clinical Indicators
Cancer	 Functional ability deteriorating due to progressive cancer.  Too frail for cancer treatment or treatment is for symptom control.

Dementia/ Frailty	 Unable to dress, walk or eat without help.  Eating and drinking less; difficulty with swallowing.  Urinary and faecal incontinence.  Not able to communicate by speaking; little social interaction.  Frequent falls; fractured femur.  Recurrent febrile episodes or infections; aspiration pneumonia.
Neurological disease	 Progressive deterioration in physical and/or cognitive function despite optimal therapy.  Speech problems with increasing difficulty communicating and/or progressive difficulty with swallowing.

	
 Recurrent aspiration pneumonia; breathless or respiratory failure.
 
 Persistent paralysis after stroke with significant loss of function and ongoing disability.

Heart/ disease	
 Heart failure or extensive, untreatable coronary artery disease; with breathlessness or chest pain at rest or on minimal effort.
 
 Severe, inoperable peripheral vascular disease.

Respiratory disease	
 Severe, chronic lung disease; with breathlessness at rest or on minimal effort between exacerbations.
 
 Persistent hypoxia needing long term oxygen therapy.
 
 Has needed ventilation for respiratory failure or ventilation is contraindicated.

Kidney disease	 Stage 4 or 5 chronic kidney disease (eGFR < 30ml/min) with deteriorating health.  Kidney failure complicating other life limiting conditions or treatments.  Stopping or not starting dialysis.
Liver disease	 Cirrhosis with one or more complications in the past year: diuretic resistant ascites; hepatic encephalopathy; hepatorenal syndrome; bacterial peritonitis; recurrent variceal bleeds.  Liver transplant is not possible.
Other conditions	 Deteriorating with other conditions, multiple conditions and/or complications that are not reversible; any treatment available will have a poor outcome.

Review Current Care and Care Planning

Status	Action Item
	Review current treatment and medication to ensure the person receives optimal care; minimise polypharmacy.

	Consider referral for specialist assessment if symptoms or problems are complex and difficult to manage.
	Agree a current and future care plan with the person and their family. Support carers.
	Plan ahead early if loss of decision-making capacity is likely.
	Record, share, and review care plans.

ECOG Performance Status Tool

GRADE	ECOG PERFORMANCE STATUS
0	Fully active, able to carry on all pre-disease performance without restriction
1	Restricted in physically strenuous activity but ambulatory and able to carry out work of a light or sedentary nature, e.g., light house work, office work
2	Ambulatory and capable of all selfcare but unable to carry out any work activities; up and about more than 50% of waking hours

3	Capable of only limited selfcare; confined to bed or chair more than 50% of waking hours
4	Completely disabled; cannot carry on any selfcare; totally confined to bed or chair
5	Dead

IPOS Integrated Palliative Outcome Scale

Item #	Assessment Area	Detailed Content / Question
1	Main Concerns	What have been your main problems or concerns? (Open-ended/Not scored)

2	Physical Symptoms	
Scoring for 10 core symptoms:
 
1. Pain2. Shortness of breath3. Weakness or lack of energy4. Nausea (feeling sick)5. Vomiting (being sick)6. Poor appetite7. Constipation
---	-------------------	--------------------------------------------------------------------------------------------------------------------------------------------------------------------------------------------------------------------------------------------------------------------------------------

		
8. Sore or dry mouth
 
9. Drowsiness
 
10. Poor mobility

3	Patient Anxiety	Have you been feeling anxious or worried about your illness or treatment?
4	Family Anxiety	Have any of your family or friends been anxious or worried about you?
5	Depression	Have you been feeling depressed?
6	Peace	Have you felt at peace?
7	Sharing Feelings	Have you been able to share how you are feeling with family or friends?
8	Information	Have you had as much information as you wanted?

9	Practical Problems	Have any practical problems (financial or personal) been addressed?
10	Respondent	Who completed this questionnaire? (Patient, Staff, or both)

Annex VII: Interview Guide for Healthcare providers

Study Title: Effectiveness and Implementation Determinants of the DINKNESH App Compared to Paper-Based Assessment Tools for Palliative Care: A Mixed-Methods Cluster Randomized Trial in Addis Ababa, Ethiopia

Target Participants: HCW from Intervention Clusters (Purposively Sampled).

Time Allotment: 60-90 minutes.

Objective: To explore HCWs' experiences, perceptions, and contextual factors (enablers and barriers) affecting the uptake and use of the DINKNESH App.

Section A: Introduction, Context, and Consent (5 minutes)

Facilitator: Welcome, thank you for taking the time to share your experience with the DINKNESH App. We are here to understand what worked and what didn't work over the last 6 weeks . There are no right or wrong answers, your honest feedback is vital to scale up this service.

- Review informed consent and confidentiality protocols (especially regarding anonymity and cluster identity).
- Ground Rule: Encourage equal participation and emphasize that we are here to discuss the system and the App, not individual performance.
- Confirm willingness to be audio-recorded.

Section B: Usability, Engagement, and Initial Experience (15 minutes)

(Focus: User experience, satisfaction, clarity of the tool.)

1. When you first started using the DINKNESH App, what were your immediate feelings or thoughts about incorporating it into your daily chronic care routine?
2. How easy or difficult was the App to learn and use initially, particularly regarding the interface and navigation?

- Probe (Usability): Were the screening tools (SPICT, ECOG, IPOS) clear?
Did the App save you time or cost you time?
- 3. What was the most useful feature of the App, and what was the most frustrating or confusing part?

Section C: Workflow Integration and Process Determinants (30 minutes)

(Focus: Systemic barriers, technical challenges, and adherence)

- 4. Can you describe how the DINKINESH App changed the order or routine of your chronic care patient follow-up visits? Did the App force you to do things you normally skip?
 - Probe (Systematic Action): Was the process of documenting a referral or a counseling session clearer with the App?
- 5. Regarding Technical Barriers: What were the most common technological difficulties you faced while using the App (e.g., poor internet connectivity, battery life, App freezing)?
 - Probe (Connectivity): Did lack of reliable internet/data coverage impact your ability to use the App in real-time during a patient visit?
- 6. Regarding Supervisory and Organizational Support: How did your facility manager or supervisor support you during the 6 weeks implementation period?
 - Probe (Systemic Enablers): Did you receive sufficient guidance or reminders? Was there any conflict between App use and other facility reporting requirements?
- 7. Regarding Workload and Time: Did the App ultimately increase or decrease your perceived workload? Was the time spent using the App compensated or recognized in any way?

Section D: Capacity, Sustainability, and Recommendations (20 minutes)

(Focus: Capacity building, attitudes, and future scalability.)

8. Thinking about the training you received, how well did it prepare you to use the App and understand the principles of systematic palliative care screening?
 - Probe (Knowledge Gain): Did you feel more confident identifying palliative care needs after using the App than you did before the study?
9. If the DINKINESH App were rolled out nationally tomorrow, what is the single biggest factor that would make HCWs continue using it for the next year? (The "Enabler")
10. Conversely, what is the single biggest factor that would cause HCWs to abandon the App and revert to paper records? (The "Barrier")
11. Final Recommendation: If you could give the DINKINESH team one piece of advice on how to improve the App for future national use, what would it be?

Annex IX: Interview Guide for Patients

Study Title: Effectiveness and Implementation Determinants of the DINKNESH App Compared to Paper-Based Assessment Tools for Palliative Care: A Mixed-Methods Cluster Randomized Trial in Addis Ababa, Ethiopia

Method: In-Depth Interview

Time Allotment: 30–45 minutes

Objective: To explore patients' experiences of the care they received, their perception of the screening process, and their satisfaction

Section A: Introduction and Consent (5 minutes)

Facilitator: Thank you for agreeing to speak with me. I am a researcher from Addis Ababa University. We are trying to improve how patients like you are cared for in home to home visits. Recently, your health care worker used a new system (an App on their phone) to ask you questions about your health and symptoms. I would like to hear your honest thoughts about that visit. This is not a test, and your answers will not affect your medical care. Everything you say is confidential.

- Review informed consent.
- Confirm willingness to be audio recorded.

Section B: Experience of the Consultation (10 minutes)

(Focus: Patient-centeredness, communication, and time)

1. Think back to your last visit with the nurse/health worker when they used the phone/tablet to ask you questions. Can you describe how that visit felt compared to usual visits?

2. Did you feel the health worker was paying attention to you, even though they were using a device?
 - Probe: Did the phone create a barrier, or did it seem to help them ask better questions?
3. The health worker asked you detailed questions about your physical symptoms (pain, tiredness) and your feelings (worry, sadness). How did it feel to be asked these specific questions?
 - Probe: Was it helpful to discuss these things? Did any question make you uncomfortable?

Section C: Perception of Action and Support (15 minutes)

(Focus: Outcome of the screening)

4. After the health worker finished the questions on the phone, what happened next? What advice or help were you given?
 - Probe: Were you referred to a hospital? Were you given new medicine? Did they just talk to you?
5. Do you feel that the action taken (referral/counseling) addressed your main problem?
6. Did you understand why the health worker made that decision? Was the plan explained clearly to you?

Section D: Satisfaction and Recommendations (10 minutes)

(Focus: Overall satisfaction and future preference)

7. Overall, how satisfied were you with the care you received during that visit?
8. If you come back for your next follow-up, would you prefer the health worker to use this system again to check your symptoms, or go back to the old way? Why?
9. Is there anything you would change about how the health worker interacted with you?

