6.2. Study Design

The primary aim is to assess the comparative rate of identification of patients with palliative care needs using DINKNESH App via a Cluster Randomized Controlled Trial , while concurrently gathering data on implementation determinants to inform future scale up .

It will use a mixed-methods cluster randomized controlled trial with two parallel arms, which are Intervention and Control. The CRCT design helps to minimize contamination. It will be a pragmatic CRCT with a 6 weeks intervention period. As the primary outcome is the process of care measure, changes are expected to be observed early following implementation.

To isolate the specific effect of the intervention from the effect of general education, Health Care Workers in both arms will receive an initial, brief baseline training session on standardized palliative care assessment. Following this training, the intervention group will proceed to use the DINKNESH application and the control paper based for the 6

weeks intervention period. Consequently, the study will measure and compare the rate of patient identification.

The qualitative component will use a post intervention exploratory design based on Focus Group Discussions with healthcare workers to understand experiences, challenges, and enablers of integrating the App into routine palliative care.

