6.5. Sampling Method

In this study, we will use multistage sampling aligned with the principles of a cluster randomized controlled trial. In the first stage, the clusters are health centers within Addis Ababa that have palliative care services through Family Health Teams. Of the 101 health centers, 95 currently deliver palliative care and will form the sampling frame. A complete list of eligible facilities will be obtained from Addis Ababa regional health bureau. To make sure the selected clusters are representative of the city, we will use stratified random sampling, stratifying facilities by patient volume. After this, these facilities will be randomly allocated to either the intervention or control group using a computer-generated sequence managed by an independent person so that there's allocation concealment. A total of 12 clusters (6 per arm) will be included in the study.

In the second stage, all patients currently diagnosed with a chronic illness and receiving follow-up home-visit care from the Family Health Teams within the selected cluster

catchment areas will be included consecutively. This population forms the denominator for the study's proportion-based primary outcome, representing the total reach of the implementation environment. Given that the screening is integrated into routine clinical care, verbal informed consent will be sought from each identified patient (or their proxy caregiver) for the research use of their data. This verbal consent will be witnessed and documented. The numerator will then be defined as the subset of these chronic patients who are successfully screened and identified for palliative care needs using either the DINKNESH App (intervention) or standard paper-based tools (control). This multistage approach ensures that the study captures real-world implementation fidelity while minimizing selection bias among the target chronic patient population.

For the qualitative component, we'll purposely identify healthcare providers and key stakeholders from facilities assigned to the intervention arm. Participants will be chosen based on their direct involvement in the rollout or oversight of the palliative care App, ensuring diversity across roles. Data will be collected through FGD organized by professional category to foster open dialogue and reduce hierarchical influence. The number of FGDs will be guided by thematic saturation, typically reached after four to six FGDs.

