6.6. Data Collection

We will use a mixed method to collect both quantitative and qualitative data, ensuring a comprehensive evaluation of the DINKNESH App's impact. For the quantitative part, data will be extracted from the DINKNESH app backend logs in the intervention arm and paper-based forms in the control arm, measuring the health care workers' documented patient identification rates and clinical action taken. All data collectors will be trained appropriately to ensure ethical conduct and will conduct weekly site visits to document the number of chronic patients visited and screened, ensure data integrity and adherence to the study protocol across all eight clusters.

For the qualitative component, we will conduct FGDs with health care workers

purposely selected from the intervention arm. This purposive identification is designed to ensure maximum variation in experience and professional role to gather both hands-on user experiences and health facility insights. The FGDs will explore user experiences, perceived usability of the App, and contextual enablers and barriers (systemic, human, and technological) affecting the App's integration into routine workflows. In depth interviews will also be made in selected identified patients in both intervention and control to compare their experiences. All discussions will be audio-recorded with consent, transcribed verbatim, and translated from Amharic into English by experienced translators.

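### The only patient interview guide shown says an App was used, so it cannot be used as written for the control-arm interviews that section 6.6 plans

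*Protocol*

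**What the plan says.** Protocol section 6.6 (Data Collection) states the purpose and reach of the patient interviews: "In depth interviews will also be made in selected identified patients in both intervention and control to compare their experiences". Section 6.8 (Data Analysis) then uses what identified patients say, together with what health workers say, to explain the quantitative result.

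The control condition is paper. Section 6.2 says "the intervention group will proceed to use the DINKNESH application and the control paper based" for the six weeks, and section 6.5 makes the same split when it defines the numerator.

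Annex IX (Interview Guide for Patients) is the instrument. Its header names patients without restricting them to an arm, and its stated objective (experience of care, perception of the screening, satisfaction) would suit either arm. The facilitator's script then says "Recently, your health care worker used a new system (an App on their phone) to ask you questions about your health and symptoms". Four questions carry the same premise:

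- Question 1: "Think back to your last visit with the nurse/health worker when they used the phone/tablet to ask you questions"
- Question 2: "Did you feel the health worker was paying attention to you, even though they were using a device"
- Question 4: "After the health worker finished the questions on the phone, what happened next"
- Question 8: "would you prefer the health worker to use this system again to check your symptoms, or go back to the old way"

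The annex gives no alternative wording and no skip instruction for control patients.

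**The concern.** The interview plan covers two arms, but the script is written for one. An interviewer who follows Annex IX in a control household makes a false statement about that patient's own care, and then asks about a device the patient never saw. An interviewer who notices the mismatch has to improvise, and the wording then differs between arms in a way that nobody controls or records. In both cases, the comparison of experiences announced in section 6.6 lacks a common instrument on several of its topics. Those answers are also meant to help explain how and why the App changed practice. Once the interviews are done, answers to mismatched questions cannot be repaired at analysis.

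**Working it through.** No figure in the protocol bears on this point. The check sets the plan, the control condition and each item of the guide side by side.

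**Step 1: who is interviewed.** Section 6.6 names both arms and gives comparison as the reason. Control-arm patient interviews are therefore planned.

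**Step 2: what control patients experienced.** Sections 6.2 and 6.5 put control clusters on paper. No control patient is planned to be assessed with the App.

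**Step 3: whether Annex IX is limited to one arm.** It carries no such line. Annex VII, the provider guide, does: it names health workers from intervention clusters as its target. The authors marked an arm restriction in one guide and not in the other.

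**Step 4: each item, read to a control patient.**

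| Item | Premise | Usable in control? |
|---|---|---|
| Introduction | App was used | No, the statement is untrue |
| Question 1 | Phone or tablet was used | No, the content depends on the device |
| Question 2 and its probe | Device was used | No, the content depends on the device |
| Question 3 | Symptoms and feelings were asked about | Yes |
| Question 4 | Phone was used | Yes, once the phone is no longer mentioned; the substance is what help or advice followed |
| Question 5 | An action was taken | Yes |
| Question 6 | A decision was made | Yes |
| Question 7 | A visit took place | Yes |
| Question 8 | New system against the old way | No, the content depends on the new system |
| Question 9 | Interaction with the health worker | Yes |

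**Step 5: count.** Three questions depend on the App (1, 2, 8), one needs a change of wording (4) and five work unchanged (3, 5, 6, 7, 9): 3 + 1 + 5 = 9. Questions 5 and 6 refer back to the action and decision raised in question 4, so they read properly once question 4 is reworded. A common core of 5 + 1 = 6 questions is then available in both arms.

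**Step 6: how many interviews are affected.** Every control-arm patient interview is affected if the guide is followed as written. Their number cannot be given, because the budget table leaves the number of in-depth interviews as X.

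**The case against.** The strongest reply is that the guide is right and the sentence in section 6.6 is the outlier. The secondary objective concerns adoption of the App, section 6.2 describes the qualitative component as focus groups with health workers, and section 6.5 draws its qualitative participants from intervention facilities. An app-specific patient guide fits that intent. This has force, and it is why the fix offers two routes. It does not remove the contradiction: section 6.6 is explicit about both arms and about comparing them, and the two texts must be reconciled one way or the other.

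A second reply is that a control version may exist. Some pages were removed from the text at hand, and Annexes VI and VIII are not shown. This cannot be excluded. However, no visible text refers to such a version, and Annex IX is not labelled as the app-arm guide.

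A reader might also infer more than the text supports:

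- *That the guide is wholly unusable in control, or that no comparison can be made.* Five questions work unchanged and a sixth needs a few words removed. These cover being asked about symptoms, what followed, whether it helped, whether it was explained, satisfaction and suggested changes, which is most of the annex's own objective.
- *That the guide reveals the allocation.* The protocol claims no blinding of patients, health workers or interviewers, and a patient can see whether a tablet or paper was used. No harm follows.
- *That the script leads respondents to favour the App.* It says the researchers are trying to improve care and that a new system was used; it does not say that the App improved care. It asks for honest views, question 2 and its probe allow that the device got in the way, and question 8 offers both options.

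**Conclusion.** The inconsistency is real and limited. As written, Annex IX puts an untrue statement to control patients, three of its nine questions do not apply to them and a fourth is misworded. The remaining five can support a partial comparison.

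The effect is confined to the patient interviews and to the part of the section 6.8 triangulation that rests on them. The primary outcome, its analysis and the sample size are untouched. The point should be corrected before interviews begin, but it does not threaten the trial's main conclusion.

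The conclusion rests on two assumptions: that section 6.6 means what it says about control-arm interviews, and that no separate control guide exists among the pages not shown. If such a guide exists, what remains is to label Annex IX as the app-arm guide and to check that the two guides share a common core.

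**What to change.** Before the first patient interview, choose one of two routes.

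1. **Keep the comparison.** Reword the introduction and question 4 so that they refer only to the questions the health worker asked at the last visit. Use questions 3 to 7 and 9 as a common core in both arms. Move questions 1, 2 and 8 to an app-arm module, and write parallel versions about the paper form for control patients.
2. **Drop the comparison.** Label Annex IX as a guide for intervention-arm patients, remove the control-arm interviews and the between-arm comparison from section 6.6, and say in section 6.8 that the patient insights come from the intervention arm only.

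The first route costs rewording one annex; the second costs a label on the annex and short edits to sections 6.6 and 6.8. Either needs an ethics resubmission. Neither changes recruitment, the sample size or the quantitative data collection.

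### The patient interview guide states what the health worker asked before any neutral question on it, so patients' accounts of the assessment are prompted

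*Protocol*

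**What the plan says.** Annex IX (Interview Guide for Patients) gives its objective as exploring patients' experience of care, how they perceived the screening, and their satisfaction. In the order a patient would hear them, the relevant items are:

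- **Section A, opening script:** "Recently, your health care worker used a new system (an App on their phone) to ask you questions about your health and symptoms".
- **Section B, question 1:** the patient is asked to think back to the visit at which the worker used a phone or tablet for the questions, and then: "Can you describe how that visit felt compared to usual visits".
- **Section B, question 3:** "The health worker asked you detailed questions about your physical symptoms (pain, tiredness) and your feelings (worry, sadness", followed by a question on how it felt to be asked. The probes cover helpfulness and discomfort.
- **Section C, question 4:** "After the health worker finished the questions on the phone, what happened next? What advice or help were you given". One of its probes is "Did they just talk to you".
- **Section C, question 5:** "Do you feel that the action taken (referral/counseling) addressed your main problem". Question 6 goes on to ask whether the patient understood the reason for the decision.

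Section 6.6 plans these interviews in selected identified patients of both arms, to compare their experiences. Section 6.8 triangulates the quantitative results with what healthcare workers and identified patients report, in order to put differences in identification and clinical action in context and explain them. The quantitative data themselves are the workers' "documented patient identification rates and clinical action taken", taken from App logs or paper forms (section 6.6).

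**The concern.** A leading statement invites agreement. When an interviewer from the university states that detailed questions on symptoms and feelings were asked, and then asks only how that felt, a patient to whom this did not happen has to correct the interviewer. Some will not. The interview material on what the assessment contained is then partly the guide's own words returned by the patient.

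This matters here because the Protocol itself expects uneven delivery. Its literature review names worker-level risks to implementation fidelity and the chance that the App is felt as an extra burden. The provider guide in Annex VII asks whether the App made workers do things they would normally skip. If the assessment was shortened in some visits, the patient interviews are a natural place to learn of it, and the present order of questions makes that less likely. Prompted accounts would then enter the triangulation and could make the assessment look more uniform, from the patient's side, than it was.

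**Working it through.** No sample size, power or other figure is involved. The check is of order and wording, and it differs for the content of the assessment and for the action that followed.

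**Content of the assessment**

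1. The script asserts that an App was used to ask about health and symptoms.
2. Question 1 repeats the premise of a device and of questions being asked. It is open, but about how the visit felt and not about what was said or done.
3. Question 2 is about whether the worker paid attention while using the device.
4. Question 3 asserts that detailed physical and emotional questions were put.

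None of the items before question 3 (the script and questions 1 and 2) asks the patient to say what was asked. Question 3 and its probes do not ask whether the questions were asked at all. Accounts of content are therefore prompted throughout.

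**Action after the assessment**

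1. Question 4 takes for granted that questions were completed on a phone, but then asks openly what happened next. This comes before any mention of an action taken.
2. Its second sentence mildly presumes that advice or help was given. The probe on whether the worker only talked leaves room for no referral and no new medicine.
3. Question 5 refers to the action taken and question 6 to the decision. Neither has a branch for a patient who has just reported nothing.

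The open question thus precedes the presuming ones. The defect is a missing branch and not a prompted answer.

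**Fit to the control arm**

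Control clusters use paper, yet control patients are to be interviewed. The script and questions 1, 2 and 4 all presuppose a phone, tablet or App. In the only patient guide shown, the asserted premise does not apply to these patients.

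**Room in the schedule**

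The section times are 5 + 10 + 15 + 10 = 40 minutes, against a stated allotment of 30–45 minutes. One or two extra minutes give 41–42, still inside the upper limit.

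**The case against.** The strongest reply is that the guide was not written to audit delivery. Its aim is experience, perception and satisfaction. Identification and action are measured from logs and forms, and weekly site visits document how many chronic patients were visited and screened. The interviewees have already been identified, so some assessment is to be expected and question 3 is not a baseless premise. Several questions are open, the script asks for honest thoughts, and a trained interviewer can adapt.

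Much of this stands, and it rules out several stronger readings that a reader might infer:

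- *That the guide asserts an action before asking what happened.* It does not: question 4 comes first, and an action that was recorded but not received could surface there.
- *That the interview is the only evidence from the patient's side.* The IPOS respondent item, "Who completed this questionnaire? (Patient, Staff, or both", allows the patient to complete that form.
- *That completion by staff shows the patient was not asked.* A worker may fill in the form from the patient's answers.
- *That the triangulation will falsely confirm the workers' records.* Section 6.8 uses the interviews to contextualise and explain differences. It does not state that they verify entries.

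What the reply does not remove is the wording of the script and questions 1 and 3. Perception of the screening is within the guide's stated aim, and what was asked is part of that. Being identified does not establish that the emotional questions were put. The site visits, as described, yield counts of patients visited and screened; section 6.6 mentions no observation of visits. Relying on the interviewer to depart from the script leaves the correction to chance.

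**Conclusion.** The point holds in a limited form. Patients' accounts of what the assessment contained are prompted, because the script and question 1 presuppose it and question 3 asserts it with no neutral question beforehand. A patient who was not asked is less likely to say so. For the action that followed, the flaw is confined to the second sentence of question 4 and to questions 5 and 6, which do not provide for a patient who reports no action.

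The possible bias falls on the qualitative component and on the triangulation, not on the primary outcome. Its size cannot be derived: the document gives no rate of incomplete assessments, and the budget leaves the number of patient interviews open. The conclusion rests on two assumptions: that interviewers follow the guide broadly as written, and that some patients will agree with an asserted premise. This is a low-severity improvement, worth making because it is almost free.

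**What to change.** Change Annex IX as follows:

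1. **Section A and question 1:** make them neutral. Refer to the recent home visit without stating that an App, phone or tablet was used to ask about symptoms. The same text then serves control patients. Keep the device wording of questions 2 and 4 for patients who report that a device was used.
2. **Before question 3:** add one open recall question, such as *Please tell me what the health worker did and asked at that visit.*
3. **Question 3:** ask how it felt only for topics the patient mentions, or confirms on a neutral probe (*Were you asked about pain? About worry?*).
4. **Questions 4 to 6:** keep the open first part of question 4, reword its second sentence to ask whether any advice or help was given, and ask questions 5 and 6 only if the patient reports an action.

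The wording change to the script and question 1 is needed for the rest to work, since a recall question asked after the present script would still be prompted. I would not add a patient-by-patient comparison of interviews with the IPOS respondent field: the Protocol describes no link between interview and form, and its ethics section has recordings transcribed and anonymised immediately.

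The cost is a short revision of the guide and a minute or two per interview, with no added participants or staff.
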